A MRI-Controlled, multicenter, Baseline-to-Treatment, 32-weeks, open-label, Phase IIa Trial in Patients with Relapsing-Remitting Multiple Sclerosis or Clinically Isolated Syndrome
- Short Title:** SABA
- Study Phase:** IIa
- Study Design:** Phase IIa study consisting of a run-in phase, a dose finding phase, a stabilization phase, a continued treatment phase and a follow-up.

The trial will consist of:

- 12 week **run-in phase** (4 monthly baseline MRIs)
- **Stage 1: Dose finding:** Treatment with Boswellic acid will be initiated by escalating the dose to the maximum individually well tolerated dose within the first 4 weeks of treatment. Dose finding period of up to 4 weeks. Safety with respect to the effect of Boswellic acid (BA) on MS/CIS will be monitored by MRI and clinical assessment. The highest individual well tolerated dose will be used for each patient in Stage 2.
- **Stage 2: Stabilization:** A phase of 4 weeks will be used for adjustment of the dose to a continuously well tolerated dose. Patients not tolerating the dose established in Stage 1 will be treated with their maximum individually well tolerated dose.
- **Stage 3: Treatment:** A phase of 6 months will follow the dose finding and stabilization phases for a total of 8 months treatment. MRI will be used as the primary outcome measure to assess safety and to determine the effect of Boswellic acid on disease activity. The mechanism of action of Boswellic acids will be examined in parallel to the MRI and clinical assessment.
- **Stage 4: Follow-Up:** A phase of 4 months will follow the treatment phase. Patients are offered to continue study drug or to stop study drug after month 8. In either case the final follow-up visit will take place at month 12 including a complete clinical and MRI assessment.

Study rationale: Boswellic acids (BA) are the main components of extracts from the resin of the frankincense tree (*Boswellia serrata*).

These BAs have known anti-inflammatory activities and have been used literally for thousands of years in traditional Eastern and Asian medicine. Recently, the molecular mechanism of action of several specific BAs has been defined as inhibition of cathepsin G, microsomal prostaglandin synthase (mPEGS)-1, and 5-lipoxygenase (5-LO), i.e. factors that are involved in cell migration, inflammation and neurodegeneration in Multiple Sclerosis.

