10 SCHEDULE OF EVENTS

10.1 Tests and evaluations

Unless otherwise specified, tests and evaluations described below for the screening visit must be performed within seven days prior to the patient's first MRI. Blood samples should be drawn as early in the day as possible, preferably at the same time of day to avoid diurnal variation and before any steroids are taken in order to avoid depletion of lymphocytes by these agents.

In the event of an MS relapse, a MRI scan will be obtained prior to initiation of steroid therapy. The next scheduled MRI scan will be delayed until at least 28 days after the end of steroid therapy. Subsequent MRI scans will occur at regularly scheduled patient visits.

Additional non-pharmaceutical studies carried out at the discretion of the investigator when deemed appropriate for optimal management of the patient must also be reported.

See Study Schedule Flow Chart (App. A) for summary of tests and evaluations by time-point.

Month -3 (Screening Visit)

Unless otherwise specified, the tests and evaluations described below must be performed within seven days prior to the patient's first MRI in order to determine

patient eligibility:

- A complete medical history.
- A complete MS history.
- Inclusion and exclusion criteria.
- A complete physical examination.
- Vital signs and body weight.
- Haematology: see 11.3.
- Blood chemistries: see 11.3.
- Hepatitis B and C Screening or Check for recent Hepatitis B and C Screening: see 11.3.
- Urinalysis: see 11.3.
- Urine pregnancy test for women of child-bearing potential.
- Recording of concomitant medication.
- EDSS, SNRS, MSFC.
- HAQUAMS, MSIS29, HADS, Fatigue Severity Scale, HARAS for each Relapse within the last 12 months
- Cranial MRI.

Month -2 (\pm 7 days)

- Monitoring of adverse events.
- Vital signs and body weight.
- Urine pregnancy test for women of child-bearing potential.
- Recording of concomitant medication.
- Cranial MRI.
- EDSS, SNRS

Month -1 (\pm 7 days)

- Monitoring of adverse events.
- Vital signs and body weight.
- Urine pregnancy test for women of child-bearing potential.
- EDSS, SNRS, MSFC.
- Recording of concomitant medication.
- Cranial MRI.

Month 0 (\pm 7 days)

- Cranial MRI (within 7 days prior to study drug administration).
- Inclusion and exclusion criteria.
- Monitoring of adverse events.
- Complete physical examination.
- Vital signs and body weight.
- Urine pregnancy test for women of child-bearing potential.
- Haematology: see 11.3.

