12.1 Adverse Events: Definition and management

The terms “relationship”, “serious” and “severity” used in this section, are defined in Table 3.

For the purposes of this study, adverse events are defined as any signs (including the clinical manifestations of abnormal laboratory results) or medical diagnoses noted by medical personnel, or symptoms reported by the patient, regardless of relationship to study drug, that:

- a) Have onset anytime after the first visit.

OR

- b) Have worsened since the event was previously reported (this includes worsening of signs, symptoms, or diagnoses that were present prior to dosing).

All adverse events reported by the patient or observed by study site personnel from the first visit until completion of a patient’s participation in the study must be recorded in the patient's file and CRFs. Serious Adverse events are to be recorded regardless of relationship to the study protocol and reported to the Sponsor.

The information to be recorded in the patient file will include, but not be limited to, relationship of the event to study drug and severity of the event. Specific instructions for recording adverse events will be provided under separate cover and will be reviewed by the study site personnel.

Patients will be given the name and phone number of personnel at the study site that can be called in the event of an emergency or to report an adverse event that is of concern to the patient. The contact information will also be displayed in the patient consent form.

Any serious adverse event (SAE, for definition see table 3) occurring during any time of the study (baseline and treatment phase) will be reported by the investigator to the Sponsor (here his deputy: the PI) immediately, but no longer than 24 hours after it becomes known.

The Sponsor will document all Severe Adverse Events (SAEs) reported by the Investigator.

The Sponsor will report all SAEs and all adverse events to the DSMB every 3 months.

The Sponsor will report all Suspected Unexpected Serious Adverse Reactions (SUSARs) to the relevant Ethics Committees and the relevant Competent Authorities at the latest 15 days after it becomes known. He will also inform all Investigators involved in the trial and the DSMB.

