12.2 Management

All adverse events reported by the subject or observed by the study site personnel from the start of the study until completion of a subject's participation

in the study (when all of the required post-dosing evaluations are completed) must be recorded in the subject's Clinical Center patient file.

Adverse events are to be recorded regardless of their relationship to the study drug.

All adverse events must be followed until the event resolves or until the subject's clinical course has stabilized, irrespectively of continuation of the study drug or the pre-specified observation period. This follow-up is also necessary if laboratory or clinical or MRI findings suggestive of a safety problem are noticed which do not fulfill the criteria of an adverse event.

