13.3 Evaluation of Safety

The safety population is defined as all subjects who received at least one dose of study drug and have at least one post-baseline assessment of the safety parameter available.

The primary objective of this study is to determine the safety and tolerability of BOSWELAN therapy in subjects with multiple sclerosis using clinical, MRI, and laboratory measures.

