13.3.1 Adverse Events

The incidence of all adverse events reported by the investigator and/or the subject will be tabulated by severity and relationship to treatment. Adverse events resulting in treatment discontinuation or dose reduction will be identified. All adverse events will be documented according to the directions given in the respective CRFs.

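### The all-event adverse event tables mix events on BOSWELAN with events from the drug-free run-in and, in patients who stop, with later off-drug events

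*Protocol*

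**What the plan says.** **Which events count.** Under Section 12.1 an adverse event qualifies, whatever its relationship to the drug, if it is among those that "Have onset anytime after the first visit". It also qualifies if it has worsened since it was previously reported, and "this includes worsening of signs, symptoms, or diagnoses that were present prior to dosing". The first visit in Section 10.1 is screening at Month -3. Adverse event monitoring is listed at Months -2, -1 and 0, and the first dose is given at Month 0.

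**When counting ends.** Section 12.1 requires recording of events reported by the patient or "observed by study site personnel from the first visit until completion of a" patient's participation. Section 12.2 describes that endpoint as the time "when all of the required post-dosing evaluations are completed". According to the Summary, "Patients are offered to continue study drug or to stop study drug after month 8", and every patient is seen at month 12. Under Section 7.3.1, patients who discontinue early are followed for 2 further months.

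**What is tabulated.** Section 13.3 states that "The safety population is defined as all subjects who received at least one dose of study drug" and adds that at least one post-baseline assessment of the safety parameter must be available. Section 13.3.1, under that heading, states: "The incidence of all adverse events reported by the investigator and/or the subject will be tabulated by severity and relationship to treatment". It also says that events leading to discontinuation or dose reduction will be identified. It sets no onset limit and no split by period.

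**The concern.** The population is restricted to people who were dosed, but the events are not restricted to time on drug. A headache in week 5 of the run-in and a headache in week 5 of treatment enter the same tabulation.

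Safety and tolerability are the primary objective (Section 3.1), and the trial is open-label with no control arm. A reader will take the all-event incidence as a description of what happens on BOSWELAN. If part of it arose before the first capsule, that description is wrong by an amount that the table itself does not reveal.

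**Working it through.** The Protocol states no adverse event incidence, so there is no figure to reproduce. The check uses the Protocol's own periods.

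**Inputs**
- Run-in: 12 weeks, taken as 3 months (Summary).
- Treatment: 8 months (Summary).
- Follow-up: 4 months, on or off drug by the patient's choice (Summary; Section 2.3, Stage 4).
- Full counting window: 3 + 8 + 4 = 15 months.

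**Step 1: untreated share of the window**
- Through month 8: 3 / (3 + 8) = 27.3%.
- Through month 12, patient continues: 3 / 15 = 20%.
- Through month 12, patient stops at month 8: (3 + 4) / 15 = 46.7% of calendar time.

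**Step 2: rise in event counts for an inert drug**

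With a constant event rate and equal ascertainment throughout, counts are proportional to months counted.
- Through month 8: 11/8 - 1 = 37.5%.
- Through month 12, continues: 15/12 - 1 = 25%.
- Through month 12, stops: 15/8 - 1 = 87.5%. This is an upper bound. Section 10.1 and Appendix A give the month 9, 10 and 11 adverse event calls only to patients who continue. Patients who stop have no scheduled adverse event contact between months 8 and 12.

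**Step 3: share of patients with at least one event**

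The Protocol gives no background rate, so this step assumes a range and no drug effect. The formula is 1 - exp(-rate × months).

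| Assumed rate per month | 8 months on drug | Run-in + 8 (11 months) | 12 months on drug | Full window (15 months) |
|---|---|---|---|---|
| 0.02 | 14.8% | 19.7% | 21.3% | 25.9% |
| 0.05 | 33.0% | 42.3% | 45.1% | 52.8% |
| 0.1 | 55.1% | 66.7% | 69.9% | 77.7% |
| 0.2 | 79.8% | 88.9% | 90.9% | 95.0% |

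Through month 8, the run-in alone adds about 5 to 12 percentage points. For patients who stop, the 15-month column is again an upper bound.

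**Step 4: does the relationship split separate the periods?**

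In Table 3, an event is not related if it lacks a reasonable time sequence *and* has a likely other cause. It is unlikely if *either* holds. A run-in event with no clear other cause is therefore rated unlikely. So is an on-drug event with plausible timing but a likely other cause. That category pools untreated and treated events. Read sensibly, the likely and definite categories exclude run-in events, because those cannot follow dosing.

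**The case against.** **A statistical analysis plan may supply the on-treatment window.** Such a plan may exist, and protocols commonly leave that detail to it. *All adverse events* could also be read as meaning no restriction by causality or by reporter. A reader might infer that the point is simply a missing treatment-emergent definition, or that the Protocol forbids such an analysis. The documents support neither. The point is narrower: the stated definition and the stated table, followed together, give a mixed figure. An analysis plan could narrow it, but the Protocol wording should then agree.

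**Section 12.1 is a collection rule.** This stands. Recording from the first visit is sound and need not change. The problem arises only when Section 13.3.1 tabulates everything collected.

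**The relationship split already protects the related-event counts.** This largely stands for run-in events, as Step 4 shows, but less clearly for off-drug months. Events leading to discontinuation or dose reduction cannot arise before dosing. The all-event totals and the severity distribution across all events remain mixed.

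**Adverse event incidence is not the whole safety answer.** This stands. Section 3.1 also names MRI, clinical and laboratory measures. Section 13.3.3 compares clinical measures at baseline with month 8 or earlier. No stopping threshold in Section 7.3.2 uses a pooled adverse event incidence. The distortion also overstates event frequency and does not conceal events, although it blurs attribution.

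**The run-in is not a clean control.** This stands too. A reader might treat the run-in rate as a within-patient comparator. But Section 5.3 delays treatment until at least 30 days after a relapse (60 days if intravenous corticosteroids were given), so entry to treatment is selected on a recent stable course.

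**Conclusion.** The point holds for the all-event and severity tabulations. As written, they include at least 12 drug-free weeks for patients who start on schedule, and longer where Section 5.3 delays the start. Through month 8 this is 27% of the counted time and, for an inert drug, 37.5% more events than in the 8 treated months. That size assumes a constant rate, equal ascertainment and full follow-up. Patients who leave treatment early would have a larger run-in share.

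Months 9-12 in patients who stop add at most 4 further months, and probably less. A reader might take 87.5% as the expected inflation for these patients, but the contact schedule supports it only as a ceiling. Nor do the documents support a conclusion that the trial's safety assessment as a whole is compromised. Counts of likely or definite events, and of events that led to discontinuation or dose reduction, are little affected. The change should be made because it touches a main table for the primary objective and is easily corrected.

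**What to change.** Leave the recording rule in Section 12.1 as it is. In Section 13.3.1:

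1. Base the incidence tables on treatment-emergent events, meaning onset or worsening from the first dose to the last dose plus a follow-up window that the sponsor chooses and states.
2. Show run-in events and off-drug events in separate columns, each with its patient-months.
3. If the run-in rate is shown beside the on-drug rate, present it as descriptive context and note that it is not a neutral comparator.

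The cost is analysis wording only, with no added visits or assessments. One condition applies: the case report form must capture onset dates and dosing dates. Section 7.4 provides for a record of titration and deviations. Section 12.1 names relationship and severity and leaves further recording instructions to a separate document, so capture of the onset date should be confirmed.

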12.2 Management

All adverse events reported by the subject or observed by the study site personnel from the start of the study until completion of a subject's participation

in the study (when all of the required post-dosing evaluations are completed) must be recorded in the subject's Clinical Center patient file.

Adverse events are to be recorded regardless of their relationship to the study drug.

All adverse events must be followed until the event resolves or until the subject's clinical course has stabilized, irrespectively of continuation of the study drug or the pre-specified observation period. This follow-up is also necessary if laboratory or clinical or MRI findings suggestive of a safety problem are noticed which do not fulfill the criteria of an adverse event.

13.1 Sample Size Considerations

Based on analyses of a natural history cohort studied with monthly MRIs for a minimum of one year, a baseline to treatment designed trial incorporating 4 baseline MRIs and 4 treatment MRIs will require 12 patients to detect a 60% reduction in Gd-enhancing lesions with an alpha of 0.05 (one-sided). Regarding BA we expect an efficacy of 40% reduction of inflammatory lesions (Gd-enhancing) and estimate that 30 patients will be required to detect a 40% reduction with a power of 0.8 and an alpha of 0.05 (one-sided). Sample size estimation is based on published statistical simulations (64).

13.2 Background/Baseline Data

All appropriate background data will be summarized by presenting frequency distributions and/or basic summary statistics (mean, standard deviation, median, minimum, and maximum).

13.3 Evaluation of Safety

The safety population is defined as all subjects who received at least one dose of study drug and have at least one post-baseline assessment of the safety parameter available.

The primary objective of this study is to determine the safety and tolerability of BOSWELAN therapy in subjects with multiple sclerosis using clinical, MRI, and laboratory measures.

13.3.1 Adverse Events

The incidence of all adverse events reported by the investigator and/or the subject will be tabulated by severity and relationship to treatment. Adverse events resulting in treatment discontinuation or dose reduction will be identified. All adverse events will be documented according to the directions given in the respective CRFs.

13.3.2 Laboratory Data

Laboratory evaluations will be assessed to determine incidence of clinically notable abnormalities that emerge during the course of the study.

13.3.3 Clinical Safety Measures

The clinical measures are the changes in EDSS, SNRS, MSFC, and relapse rate. EDSS score will be obtained monthly as long as patients are treated with BOSWELAN either clinically or by telephone according to (62). The analyses will follow the same sequence of analyses as described for MRI. Comparison will always be made between baseline (week 0) and month 8 or earlier if treatment is stopped early.

14. Evaluation of Efficacy

Three efficacy populations will be analyzed for the primary outcome measures total Gd enhancing lesions and lesion volume:

The primary outcome in Stage 2 will first compare lesion (Gd-contrasting lesions) frequency (mean number of lesions) and area occurring during the 4 month baseline to lesion frequency and area occurring during months 5, 6, 7, 8 on treatment in patients treated with a dose of at least 800 mg t.i.d.

A secondary analysis will compare lesion frequency occurring over the 4 months of baseline to that occurring during over all treatment months.

An intention-to-treat analysis will be performed with all patients, all time on study.

Wilcoxon signed-rank test will be used for analysis of the primary endpoints.

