The individual well tolerated dose from Stage 1 will be used for each patient in a subsequent 4-week stabilization phase during which the dose will be observed for continuous safety and toleration. Afterwards this individual maximal well tolerated dose will be used in Stage 3 of the study for further 6 months. Patients not tolerating the minimum dose of 800mg t.i.d. will be excluded from the study.

Stage 3

In Stage 3 of the study, patients will be treated with their individual well tolerated dose of BOSWELAN as assessed in Stage 2 subsequently for six months. The minimum dose for patients to be considered evaluable in the primary statistical analysis will be 800mg t.i.d..

The primary outcome will assess the change in mean Gd-enhancing lesion number from the baseline to that observed over months 5, 6, 7 and 8 since a delay in treatment effect is expected. In addition to MRI evaluation, patients will have monthly neurological evaluations and immunological assessment.

Stage 4

After completing Stage 3 patients are offered to continue their BOSWELAN dose for 4 months or to stop drug intake after month 8. In any case patients are seen for clinical and MRI-follow-up at month 12 at the study center.

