7.3.1 Subject Withdrawal from the Study

A subject *must* permanently discontinue study drug treatment and *must* be withdrawn from the study prematurely for any of the following reasons:

The subject becomes pregnant. Treatment must be *immediately* discontinued. The pregnancy must be reported to the study center (study coordinator/treating physician/PI) immediately. Information about the subject, the subject's pregnancy, the outcome of the pregnancy, and the status of the infant at 8 to 12 weeks of age will also be collected.

The subject desires to discontinue study drug treatment under this protocol. Patients have the right to withdraw from the study at any time and for any reason. The investigator also has the right to withdraw patients from the study in the event of an intercurrent illness, non-compliance after a prescribed procedure, protocol violations, administrative reasons, other reasons.

The subject receives or wishes to start any restricted medication listed in table 2 except corticosteroids.

At the discretion of the investigator for medical reasons or for non-compliance.

The study will be prematurely terminated for an individual if an exclusion criteria occurs during the study.

Dosing in stage 1 has to be discontinued in case of a SAE. If dosing is stopped for greater than 2 weeks, the study medication will be stopped in that patient and the patient will be withdrawn prematurely from the study.

The reasons for discontinuation of the study drug must be recorded in the subject's Clinical Center patient file and the respective case report forms (CRFs).

Patients discontinuing dosing will be followed for an additional 2 months. If discontinuation was because of a serious adverse event, the patient will be followed until the event is resolved or stabilized, but not shorter than 2 months.

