7.3.2 Stopping Rules for Individual Patients and for the Study

7.3.2.1 Stopping Rules for Individual Patients

MRI Safety Criteria

Regarding stopping rules, we apply stipulations that we have previously applied in other trials of this kind (39, 40). Dosing will be discontinued in patients showing an increase in total Gd-enhancing lesions beyond 6 standard deviations of the mean lesion frequency during baseline plus 10 lesions. The maximum lesion number allowed, before treatment will be stopped, is 40 Gd-enhancing lesions. The upper margin (40 Gd-enhancing lesions) stems from a systematic review of the numbers and distribution of contrast-enhancing lesions derived from the placebo cohorts of pivotal phase III trials, which was performed by the Sylvia Lawry Center for MS Research ([name] and colleagues). Furthermore, if in the opinion of the investigators there is a change in appearance of enhancing lesions inconsistent with the patient's previous MRIs, e.g. change in average lesion size from small to substantially larger lesions, dosing will be discontinued.

Clinical Safety Criteria

Two clinical safety criteria will also be used as stopping criteria for each individual patient:

Clinical criterion 1 - relapses: Two or more confirmed relapses/exacerbations. A relapse/exacerbation is defined as the appearance of any new symptom or worsening of previous symptoms associated with significant changes in signs lasting longer than 24 hours and not accompanied by a rise in temperature or infection ("pseudoattack" modified after Schumacher (51)).

Single paroxysmal events (such as a tonic spasm) do not constitute a relapse, but multiple episodes occurring over not less than 24 hours do.

Treatment of relapses will be conducted according to the recommendations of the German Neurological Society (DGN)(section 7.5.3).

or

Clinical criterion 2 - progression: Worsening of two or more points on the EDSS scale for 3 months during the treatment phase, compared to baseline in the first 3 months before treatment. For patients with an EDSS score of 5.5 at study entry, a worsening of one point on the EDSS scale for 3 months during the treatment phase will lead to halt of study treatment.

Patients, who discontinue study medication due to one of the above mentioned stopping rules, will be advised to start on one of the established disease-modifying treatments according to the recommendations of the German Neurological Society (DGN).

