7.5.2 Therapies not allowed during Treatment

Any of the drugs mentioned in table 2 except corticosteroids are not allowed during the study participation. Before any treatment except the study drug is initiated, the patient or her/his outside physician should contact the study center to seek advice, if any safety issue might arise. This does not hold true for emergency cases.

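### The intention-to-treat MRI analysis takes all time on study, so off-drug scans, and possibly scans on a licensed drug, count as BOSWELAN time in a single-arm comparison (supporting analysis only)

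*Protocol*

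**What the plan says.** Section 14 lists three analyses of the lesion outcomes. The first compares baseline with months 5 to 8 on treatment, in patients on at least 800 mg t.i.d. The second compares baseline with all treatment months. The third reads: "An intention-to-treat analysis will be performed with all patients, all time on study".

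Several other passages decide which scans that third set contains:

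- Section 2.3, Stage 4: "After completing Stage 3 patients are offered to continue their BOSWELAN dose for 4 months or to stop drug intake after month 8". Either way there is a clinical and MRI visit at month 12, which section 10.1 combines with the early-termination visit.
- Section 7.3.2.1 (individual patients) stops dosing for a lesion surge, for relapses ("Clinical criterion 1 - relapses: Two or more confirmed relapses/exacerbations") or for EDSS progression. Such patients "will be advised to start on one of the established disease-modifying treatments according to the recommendations of the German Neurological Society (DGN").
- Section 7.3.1: "Patients discontinuing dosing will be followed for an additional 2 months". The same section makes withdrawal from the study mandatory when this applies: "The subject receives or wishes to start any restricted medication listed in table 2 except corticosteroids".
- Section 7.5.2: "Any of the drugs mentioned in table 2 except corticosteroids are not allowed during the study participation". Table 2 includes interferon beta, glatiramer acetate and natalizumab.

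By contrast, section 13.3.3 ends the clinical comparisons at month 8, or earlier if treatment stops early.

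**The concern.** In a randomised trial, counting all follow-up whatever treatment is taken can be defended, because both arms are treated alike. Here each patient is compared only with his or her own baseline. A scan made after washout, or on another effective drug, goes straight into the figure that will be read as the effect of BOSWELAN.

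The two kinds of scan can pull in opposite directions. If BOSWELAN works, a washout scan dilutes the effect. A scan on a licensed drug flatters it, and does so in the patients who did badly enough to be stopped. The result would be hard to interpret, although it carries the intention-to-treat label that readers tend to trust most.

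**Working it through.** **1. Scan count (section 10.1).** Cranial MRI after baseline is listed at months 1, 2, 3, 5, 6, 7 and 8, which is 7 scans, and at month 12, which makes 8. Month 4 is a telephone contact. For a patient who stops at month 8, the off-drug share is 1/8 = 12.5%. Section 4 speaks of monthly MRI; if a month-4 scan were added, the share would be 1/9 = 11.1%.

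**2. Which analyses take in that scan.**

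| Analysis | Month-12 scan off drug | Scan on a licensed drug after stopping |
|---|---|---|
| Primary, months 5 to 8 on treatment | no | no |
| Secondary, all treatment months (section 1 adds that these are on treatment) | no | no |
| Intention-to-treat, all time on study | yes | yes, if one is made |

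Because the all-treatment-months analysis already exists, the natural reading of the third is that it reaches beyond treatment.

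**3. Size of the washout effect.** Let m be a patient's mean change over the 7 scheduled treatment scans and w the change at month 12. The all-time mean change is (7m + w)/8. If activity is back at baseline by month 12 (w = 0, an assumption), this is 7m/8, however the effect is spread over months 1 to 8. Taking the planned 40% reduction as m, and letting a share s of patients stop at month 8 while the others hold the same reduction to month 12, the all-time figure is 40% × (1 − s/8):

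- s = 0.25: 38.75%
- s = 0.50: 37.5%
- s = 1: 35%

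The document gives no value for s.

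**4. Size of a rescue effect (assumed counts, for illustration).**

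- Surge: baseline mean 2, scans 2, 2, 2, then 42, which exceeds the cap of 40. On-drug mean 48/4 = 12.0, change +10. One later scan of 2 on a licensed drug gives 50/5 = 10.0, change +8. The mean falls by 1 − 10/12 = 17%, but the sign is kept. The signed-rank statistic moves only if another patient's absolute change lies between 8 and 10.
- Relapses: baseline mean 2, scans 2, 2, 3, then dosing stopped. Mean 7/3 = 2.33, change +0.33. One later scan of 0 gives 7/4 = 1.75, change −0.25. The sign flips, and the patient now counts as improved.

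**5. How many patients.** Under the cumulative hold rules in section 7.3.2.1 (study), a hold follows the fifth MRI stop or the third clinical stop. Up to 4 + 2 = 6 patients, or 6/30 = 20% of the planned 30, could therefore be stopped before such a hold. This is what those thresholds allow, not a forecast. It does not say how many would take up a licensed drug or be scanned on it.

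**6. The withdrawal passages side by side.** A stopped patient is advised to start a drug that 7.5.2 bars during study participation. Wishing to start it forces withdrawal under 7.3.1. The 2-month follow-up sentence closes 7.3.1. The text does not say whether those two months are study participation (so that 7.5.2 applies) or time on study (so that section 14 counts them).

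**The case against.** The strongest reply is that counting all follow-up regardless of treatment is what intention-to-treat means, that leaving out post-rescue scans is a choice of estimand, and that the exact window could be settled in an analysis plan not seen here. Part of this stands. Dropping post-rescue scans belongs in a sensitivity analysis, not in the main intention-to-treat result. But the protocol itself fixes the window as all time on study, and a later plan that ended it at month 8 would depart from that wording.

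It can also be said that month 12 lies outside the trial, since the title gives 32 weeks and section 10.1 labels the visit an extension. Against that, section 1 lists Stage 4 among the trial's stages and section 15 gives a study duration of up to 12 months.

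A reader might infer three stronger things that the documents do not support:

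- **That the main result is biased.** It is not: the primary and all-treatment-months comparisons are confined to on-treatment scans.
- **That stopped patients are lost to safety follow-up.** The 2-month sentence can be read as what follows withdrawal. Section 12.2 also requires adverse events, and laboratory, clinical or MRI findings that suggest a safety problem, to be followed whether or not study drug continues.
- **That a site cannot obey all the rules.** Stop dosing, withdraw, advise, then follow for two months is a workable order, and 7.5.2 is headed as applying during treatment. The body of 7.5.2 refers to participation, so the ambiguity is real but small.

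**Conclusion.** The point holds for the intention-to-treat MRI analysis only. As written, that analysis counts one off-drug scan in eight for each patient who stops at month 8. If activity has returned to baseline by month 12, this shrinks such a patient's apparent mean change by one eighth. It also admits any scan made on a licensed drug after dosing stops. The size of that part cannot be stated: the number of rescued patients is unknown, no MRI schedule is given for the 2-month follow-up, and the early-termination scan could come before the new drug. The illustrations rest on assumed counts; they show that one rescue scan can reverse a patient's direction of change, but also that a large surge barely moves a signed-rank test. The net bias could go either way. The conflict between 7.3.1, 7.3.2.1 and 7.5.2 is minor and needs reconciling. Overall this is a minor point that should be fixed, because fixing it costs almost nothing.

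**What to change.** 1. In section 14, end the intention-to-treat window at the month-8 scan, in line with the limit that section 13.3.3 sets for the clinical measures. Keep stopped patients in the analysis, including the scan that triggered stopping.
2. Report month-12 scans descriptively, separately for patients who continued BOSWELAN and those who stopped.
3. Add a sensitivity analysis that leaves out scans after the first dose of a Table 2 disease-modifying drug. Section 7.5.4 already has all medication recorded to the end of the study whether or not study drug continues, so no new data field is needed.
4. Reconcile 7.3.1, 7.3.2.1 and 7.5.2 on whether the Table 2 restriction applies after the last BOSWELAN dose, and whether the 2-month follow-up continues after withdrawal. Which clinical rule should hold is for the sponsor and investigators.

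Cost: protocol wording and one extra analysis, with no added visits or patients. The intention-to-treat mean loses one scan per patient who attends month 12, including an on-drug scan in those who continued, and the result may become slightly less or slightly more favourable.
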